3.6. Pharmacokinetic (PK) and Immunogenicity (IM) Analysis

3.6.1. PK Analysis

The plasma pharmacokinetics of ISIS 757456 (as total full-length oligonucleotides or ISIS 757456-equivalent, ISIS 757456-eq.) will be assessed following SC administration(s). PK analysis summary will be based on PK set.

Metabolite identification and profiling may be determined in some of the collected plasma samples and will be reported separately.

Plasma Concentration Data of Total Full-Length Oligonucleotides

Plasma concentrations of ISIS 757456 (ISIS 757456eq.), along with the scheduled (nominal) and actual sample times (i.e., time from SC dosing) will be listed (when applicable) for each patient, by treatment group, actual dose, subject IM status and study day. In addition, percent differences between scheduled and actual sampling times will also be listed for all patients, as well as percent differences between actual administered dose and nominal dose.

ISIS 757456 concentrations will be summarized using descriptive statistics by treatment, dose, cohort, study day, and scheduled time point, without and with stratification by IM status. Plasma

concentrations below the lower limit of quantification (LLOQ) will be indicated by "BLQ". For the purpose of calculating typical descriptive statistics (n, mean, SD, SE, %CV, geometric mean, geometric %CV, median, minimum, and maximum) for plasma concentrations, all BLQ values will be set to zero. Mean plasma concentrations that are BLQ will be presented as "BLQ", and the SD and %CV will be reported as not applicable. Other stratifications may also be performed if deemed warranted to properly interpret the pharmacokinetic analysis. At the discretion of the pharmacokineticist and/or biostatistician, samples may be excluded from descriptive statistics if there are large deviations between scheduled and actual sampling times, or large deviations between actual dose and nominal dose (> 30%).

Plasma Pharmacokinetic Parameters

The plasma PK of ISIS 757456 (as total full-length oligonucleotides) will be assessed following the SC administration. Non-compartmental PK analysis of ISIS 757456 (total full-length oligonucleotides) will be carried out on each individual subject data set using Phoenix WinNonlin version 8.0 or higher (Pharsight Corporation, Mountain View, CA). For calculation of PK parameters, all BLQ values will be set to zero. The plasma PK parameters for ISIS 757456eq. will be calculated based on actual sampling times. Since only trough and post-treatment follow up PK samples (and optional samples 2 hours post-dose on Day 1 and Day 78) are to be collected, only the following PK parameters will be calculated:

- C_{trough}
- $t_{1/2\lambda z}$

The terminal half-life shall be determined over a time interval equal to at least $1.5 \times t_{1/2\lambda z}$ (Span > 1.5). In addition, a minimum of three data points in the elimination phase will be used to define λ_z , and the coefficient of determination (r^2 _adjusted) shall be greater than or equal to 0.8 for the estimate to be accepted. Other plasma PK parameters, as appropriate, may be determined or calculated at the discretion of the PK scientist.

Plasma PK parameters will be listed by treatment, dose, subject ID, subject IM status, and study day; and appropriately summarized using descriptive statistics (n, mean, SD, SE, %CV, geometric mean, geometric %CV, median, minimum, and maximum) by treatment and study day. Additionally, subject IM status stratified plasma PK parameters will be similarly summarized. Other stratifications may also be performed if deemed warranted at the discretion of the pharmacokineticist and/or biostatistician.

3.6.2. Pharmacokinetic/Pharmacodynamic Exposure-Response Analysis

Exposure-response correlations may be explored graphically between plasma exposure (e.g., C_{trough} ,), and selected PD measures (e.g., plasma AGT level), other relevant biomarkers (such as plasma renin activity, angiotensin II, etc.) and relevant clinical endpoints (such as systolic blood pressure). In addition, the relationship between serum AGT level with plasma concentrations (C_{trough}) of ISIS 757456 eq. may be further evaluated with an inhibitory effect E_{max} model. The analysis may include stratification by IM status as well.

Population PK and PKPD analysis may be performed using the PK and PD data from this Study, and/or combined with other ISIS 757456 clinical PK/PD data from any previous and future studies in the development timeline.

3.6.3. IM Analysis

Samples collected at pre-dose on Study Days 1 (baseline), 15, 29, 57 and anytime on Days 85 and 169 in the post-treatment period will be analyzed for anti-ISIS 757456 antibodies.

Sample Level ADA data

An evaluable sample will be designated 'IM positive' based on both positive screening and confirmation assay results (i.e., confirmed positive result), and otherwise will be deemed 'IM negative'. Sample IM results (screen positive/negative, confirmed positive/negative or unevaluable, and when applicable, titer of anti-ISIS 757456 antibodies) before, during, and after treatment with study drug (sample IM status) will be listed by treatment, dose, and day of collection.

The sample ADA incidence (number) and incidence rate (percent) at each evaluated study time point will be determined and appropriately summarized by treatment and dose as the total number of and percentage of evaluated subjects with sample ADA negative, positive, and unknown status. Furthermore, titer over time will be also appropriately summarized (using descriptive statistics) as median, quartiles (25% and 75%), and range by treatment and dose.

Subject Level ADA Data

Subject's overall ADA status will be defined as 'Positive' if they have at least one confirmed positive sample result at any time during the treatment or post-treatment evaluation periods; 'Negative' if all evaluated ADA sample results during the treatment and post-treatment evaluation periods are ADA negative and they have at least one evaluable ADA result collected post study drug treatment. Otherwise, a study subject will be assigned 'Unknown' ADA status.

Furthermore, subjects with overall positive ADA status will be further classified into different ADA types based on their baseline ADA status and change in ADA titer post treatment as described below (Shankar et al. 2014):

- Treatment-Emergent ADA: sum of treatment-induced ADA and treatment-boosted ADA as described below:
 - Treatment-Induced ADA: ADA developed de novo (seroconversion) following biologic drug administration (i.e., formation of ADA any time after the initial drug administration in a subject without pre-existing ADA, i.e., baseline negative ADA)
 - Treatment-Boosted ADA: pre-existing ADA that were boosted to a higher level following biologic drug administration (i.e., any time after the initial drug administration the ADA titer is greater than the baseline titer by a factor of 8-fold or more)
- Treatment-Unaffected ADA: pre-existing ADA that were not affected (boosted) following biologic drug administration (i.e., any time after the initial drug administration the ADA titer is 4-fold or less)
- ADA type would be not applicable (NA) if the subject's overall ADA status is negative.

Other subject level IM parameters to be calculated/defined may include but not limited to:

- Subject ADA Status at Baseline: "Positive" if the subject has Week 1 Day 1 pre-dose sample (baseline) tested as confirmed positive; "Negative" if the subject has Week 1 Day 1 pre-dose sample (baseline) tested as confirmed negative; "Unknown" if the subject has Week 1 Day 1 pre-dose sample (baseline) unevaluable.
- Onset of ADA: i.e., the first day ADA positive sample observed, will be calculated by: the date of first sample has "positive" sample IM status first dose date +1
- Last Positive ADA Study Day: defined as the last positive ADA sample observed from the start of study drug treatment and will be calculated by: the date of last sample has "positive" sample IM status first dose date +1
- Last IM Sampling Study Day: defined as the last ADA sample collected from the start of study drug treatment and will be calculated by: the date of last sample collected first dose date +1
- Peak titer: the highest titer observed for the subject
- Time to peak titer: the time to reach peak titer will be calculated by: the date of first peak titer observed- first dose date +1
- Total number of ADA Positive Samples: the total number of ADA samples being confirmed positive for the subject
- Total number of ADA Samples evaluated: the total number of ADA samples being collected and analyzed successfully with reportable results for the subject

Lastly, subjects with positive ADA status may further be classified as being transient or persistent ADA response, if there are sufficient number of subjects with transient ADA status. Transient and persistent ADA definitions are defined below and based on (Shankar et al. 2014):

Transient ADA response:

- Treatment-induced ADA detected only at one sampling time point during the treatment or follow-up observation period (excluding the last sampling time point, which will be considered persistent unless shown to be undetectable at a later time) or
- Treatment-induced ADA detected at two or more sampling time points during the treatment (including follow-up period if any), where the first and last ADA-positive samples (irrespective of any negative samples in between) are separated by a period less than 16 weeks, and the subject's last sampling time point is ADA-negative.

Persistent ADA response:

 Treatment-induced ADA detected at two or more sampling time points during the treatment (including follow-up period if any), where the first and last ADA-positive samples (irrespective of any negative samples in between) are separated by a period of 16 weeks or longer or • Treatment-induced ADA detected only at the last sampling time point of the study treatment period or at a sampling time point with less than 16 weeks before an ADA-negative last sample.

The subject level ADA prevalence, incidence, and positive ADA response being transient or persistent (if applicable) will be calculated as the number and the proportion (percent) of the study population during the study period by treatment and dose. Subject level IM parameters (as described above) will be listed by treatment and dose for all evaluable subjects, and also appropriately summarized (using descriptive statistics) as median, quartiles (25% and 75%) and range, by treatment and dose.

Evaluation of IM Impact on PK, PD, Efficacy and Safety

The impact of IM on PK and PD will be evaluated by stratifying plasma PK parameters, plasma trough and post-treatment ISIS 757456 concentrations and PD biomarker levels by subject ADA status, summarized using typical descriptive statistics, and presented graphically and/or in tables. The impact of IM may also be evaluated on selected clinical efficacy end points and safety measures.

Lastly, other stratifications (e.g., based on antibody titer, onset of ADA, etc.) of selected PK, efficacy and safety assessments may also be performed if deemed warranted at the discretion of the pharmacokineticist, medical monitor, and/or biostatistician.

3.7. Safety Analyses

The safety analysis will be conducted on the Safety Set.

3.7.1. Exposure

Total amount of study drug (Placebo, ISIS 757456 80 mg or ISIS 757456 120 mg) received (mg), total number of doses administered, and treatment duration will be summarized by the treatment group.

The treatment duration will be defined as the total number of days a subject is known to be followed on study calculated as follows:

Treatment duration = Last dose date - Date of first dose + 1

3.7.2. Adverse Events

The number and incidence of adverse events (AEs) will be summarized by Medical Dictionary for Regulatory Activities (MedDRA) version 24.0 preferred term (PT) and system organ class (SOC) for:

Any treatment emergent adverse events (TEAEs).

Serious TEAEs (Treatment-emergent SAEs).

Related TEAEs and SAEs. Related is defined as "Related", "Possible", or missing relationship to study drug.

Any TEAEs by severity. At each severity level of subject summarization, a subject is classified according to the highest severity if the subject reported one or more events. AEs with missing severity will be categorized as "Missing" for this summary.

TEAEs leading to permanent study drug discontinuation.

Serious and non-serious AEs that lead to study discontinuation or investigational drug discontinuation will be listed separately. Non-treatment emergent adverse event will be included and be noted in the subject AE listing.

TEAEs will be defined as those adverse events that either start or worsen in severity on or after the date/time of first dose of study treatment.

In addition, if severity of an AE changes during the study, a separate AE will be recorded for each severity on the AE CRF. "first" and "second" AE will be identify based on AE start date. AE start date of the second record is AE stop date of first record. These linked events will be identified based on "Formlink" dataset and compared pairwise, and consider two cases, where the AE severity (mild/moderate/severe) are compared between the two records in the pair.

Case 1: The first AE record in the pair occurs before first dosing, and the second AE record occurs after first dosing.

If the AE severity or seriousness of the second record is worse than that of the first record, then only the second AE is deemed as a TEAE. Otherwise, neither record is considered as TEAE.

Case 2: Both AE records in the pair occur after first dosing.

Only the worst AE will be deemed as one TEAE.

All TEAEs identified based on the rules above will be summarized in the event number analysis.

The most conservative approach will be used to determine if the event occurs after the treatment. For example, if the onset date or resolution date of an AE is prior to the first study treatment date, it will be considered to have occurred prior to the study period. If the onset or resolution date of an AE is a partial date with only month or year available or complete missing, then the event is assumed to be within the study period unless the year is prior to the year of the first study treatment date, or if in the same year, the month is prior to the month of the first study treatment date.

Addition summary of hypotension and hyperkalemia incidence will be provided.

Local Cutaneous Reactions at the Injection Site

Local cutaneous reaction at injection site (LCRIS) is defined as (A) moderate or severe adverse events with the PTs Injection site erythema, Injection site swelling, Injection site pruritus, or Injection site pain that started on the day of injection, persisted for at least two days or ongoing; or (B) any AE at the Study Drug injection site, regardless of severity, that leads to discontinuation of study drug, where AE at the Study Drug injection site is the principal reason for discontinuation.

Percentage of injections leading to LCRIS will be calculated as follows for each subject: (A/B)*100, where A = number of injections with an LCRIS, and B = total number of injections. Doses that are split across multiple injections are counted as a single injection

LCRIS will be summarized using the MedDRA coding system, by SOC/PT. Percentage of the injections leading to LCRIS at injection site will also be summarized.

LCRIS will be listed by preferred term.

Flu-like Reactions

Flu-like reactions are defined as adverse events with PTs including either (A) Influenza like illness or (B) Pyrexia or Feeling hot or Body temperature increased, plus at least two of the following symptoms with the PTs: Chills, Myalgia, or Arthralgia, starting on day of injection or the next day.

Percentage of injections leading to flu-like reactions will be summarized using the descriptive statistics.

Percentage of injections leading to flu-like reactions will be calculated as follows for each subject: (A/B)*100, where A = number of injections leading to flu-like reactions, and B = total number of injections.

FLRs will be summarized using the MedDRA coding system by SOC/PT. Percentage of the injections leading to FLRs at injection site will also be summarized.

FLRs will be listed by preferred term.

AE of Special Interest (AESI): Platelet reduction

Per protocol, severe reductions in platelet count < 50,000/mm³ accompanied by a clinically relevant bleeding event or platelet count of < 25,000/mm³ independent of a clinically relevant bleeding event are considered as AESI. The AEs meeting the AESI criteria will be captured in the AE CRF page with a check box to indicate.

AESI will be summarized using the MedDRA coding system, by SOC/PT. A listing of AESI will also be generated.

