9.4.3.3. Action Taken with Study Drug

Action taken with Study Drug (ISIS 757456 or placebo) due to the event is characterized by one of the following.

- **None:** No changes were made to Study Drug (ISIS 757456 or placebo) administration and dose
- **Not Applicable:** SAE/AE was reported during Screening Period prior to Study Drug administration
- Permanently Discontinued: Study Drug was discontinued and not restarted

- Temporarily Interrupted, Restarted Same Dose: Dosing and/or dosing frequency was temporarily interrupted/changed or delayed due to the AE and restarted at the same dose
- **Reduced Dose:** Dosing was reduced, temporarily interrupted, or delayed due to the AE and restarted at the next lower dose or reduced dosing frequency

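### Local injection-site reactions that start mild and worsen after the injection day fail LCRIS criterion (A), because SAP 3.7.2 dates each severity record separately and defines no episode; two TEAE tables share the gap in a narrower form

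*Combined protocol and SAP*

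**What the plan says.** SAP 3.7.2 (Adverse Events) sets the recording rule: "if severity of an AE changes during the study, a separate AE will be recorded for each severity on the AE CRF". It dates the later record from the change and not from the original onset: "AE start date of the second record is AE stop date of first record". Linked records are found through the Formlink dataset and taken in pairs, "where the AE severity (mild/moderate/severe) are compared between the two records in the pair". When the first record precedes dosing and the second follows it (Case 1), the second is a TEAE only if severity or seriousness has worsened. When both follow dosing (Case 2), "Only the worst AE will be deemed as one TEAE". The SAP adds that "All TEAEs identified based on the rules above will be summarized in the event number analysis".

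No sentence says which onset date, stop date, relationship or action taken the surviving TEAE carries.

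The same section defines LCRIS in two ways. Criterion (A) covers moderate or severe injection-site erythema, swelling, pruritus or pain "that started on the day of injection, persisted for at least two days or ongoing". Criterion (B) covers "any AE at the Study Drug injection site, regardless of severity, that leads to discontinuation of study drug", where that event is the main reason for stopping. Both are written for adverse events, not for TEAEs. The section also tabulates related TEAEs and TEAEs that led to permanent discontinuation, and it lists AEs leading to discontinuation separately. Protocol 9.4.3.3 defines the permanent stop action as "Study Drug was discontinued and not restarted", and that action is recorded per event.

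**The concern.** A patient has one reaction, but the database may hold two or three records of it. Criterion (A) asks three things at once: grade, start on the injection day, and duration. After the split, no single record need satisfy all three, even when the reaction as a whole does.

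The pattern is plausible. Protocol Appendix D grades injection-site pain or edema as moderate when it lasts more than 24 hours. If the site opens a new record when that point is reached, the moderate record cannot start on the injection day.

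The same lack of an episode rule affects any TEAE table that depends on an attribute other than severity. If drug is stopped on one record and a more severe linked record becomes the TEAE, the SAP does not say whether the stop goes with it. These tables are part of how tolerability will be judged for 80 mg and 120 mg against pooled placebo.

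**Working it through.** The plan states no figure on this point, so there is nothing to reproduce. The check applies the written rules to hypothetical linked records.

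**LCRIS criterion (A).** The injection is on Day 1. A record or episode qualifies if its grade is at least moderate, it starts on Day 1 and it lasts at least two days. The SAP does not say whether duration is stop minus start or counts both end days, so both were tried.

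| Linked records | Worst record only | Each record separately | Merged episode |
|---|---|---|---|
| Mild Days 1–2, moderate Days 2–4 | No | No | Yes |
| Moderate Days 1–2, severe Days 2–4 | No | Depends on day count | Yes |
| Moderate Days 1–2, mild Days 2–5 | Depends on day count | Depends on day count | Yes |
| Mild and moderate both from Day 1, ending Day 4 | Yes | Yes | Yes |
| Moderate Days 1–4, mild Days 4–9 | Yes | Yes | Yes |

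- Row 1: the mild record fails on grade and the moderate record fails on start day (2, not 1). Keeping both changes nothing. The episode starts on Day 1, reaches moderate and lasts 4 − 1 = 3 days, so it qualifies.
- Rows 2 and 3: the moderate record lasts 2 − 1 = 1 day by difference (fails) or 2 − 1 + 1 = 2 days inclusively (passes).
- Rows 4 and 5: every method agrees.

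**Discontinuation as a TEAE.**

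- Moderate, then mild, with the stop on the mild record: the moderate record survives Case 2 and carries no stop. The event is missed.
- Moderate with the stop, later severe: the severe record survives. If it does not repeat the action, the event is missed.
- Mild, then moderate, with the stop on the moderate record: the event is counted.

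The related-TEAE table behaves the same way, but only if linked records carry different relationship ratings. A missing rating already counts as related.

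**Chains of three.** Compare consecutive pairs in severe, mild, moderate. The first pair keeps severe and the second keeps moderate, so two TEAEs survive from one episode, which is an over-count. Moderate, mild, severe does the same. In mild, moderate, severe, the moderate record wins one pair and loses the next, and no rule settles its status.

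**Meaning of worst.** Case 1 uses severity or seriousness. Case 2 does not say which governs when they disagree.

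**Size per event.** Protocol 3.4.2 plans 12 doses, and the SAP counts a split dose as one injection. One missed LCRIS therefore moves that patient's percentage by 100/12 = 8.3 points. Each active group has 150 × 1/2 × 2/3 = 50 patients, so one discontinuation missing from the TEAE table is 1/50 = 2 percentage points in that table.

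**Total size.** If a share f of LCRIS episodes reaches moderate only after the injection day, the tabulated rate is the episode rate × (1 − f), before other losses. The documents give neither quantity.

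**The case against.** A reader might infer that Case 2 discards the onset date, causality and stop action of the other record, so that LCRIS, flu-like reactions and discontinuations are all under-counted, and more so at 120 mg. The documents do not support that.

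- LCRIS and flu-like reactions are defined on adverse events, so Case 2 need not touch them. In the main example the split alone causes the miss.
- Flu-like reactions have no severity threshold and accept onset on the injection day or the next, so a mild Day 1 record already meets the timing. It would be lost only if the derivation were confined to surviving TEAEs and the worsening came later than the next day.
- The SAP is silent on attributes; it does not order their deletion. The collapse is named only for counting events, and the Formlink links keep the episode onset recoverable.
- No discontinuation vanishes from the report. SAP 3.2.4 tabulates early treatment discontinuation with its reason, the AE listing is not limited to TEAEs, and criterion (B) applies whatever the severity.
- Patient-level incidence and highest severity survive if the linked records share a preferred term.
- Nothing gives the frequency of grade changes, overall or by dose.

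All of this stands, and it narrows the point. It does not answer the first row of the table, where the written rules give a different count from the episode. One could reply that criterion (A) is meant only for reactions already moderate on the injection day. That sits badly with Appendix D, where pain or edema becomes moderate by lasting more than 24 hours.

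**Conclusion.** The concern holds in a limited form. On a record-level reading, criterion (A) misses reactions that start mild on the injection day and reach moderate or severe on a later day, and the SAP gives no instruction to read it otherwise. The tables of TEAEs leading to permanent discontinuation and of related TEAEs can miss an event only when the stop action or causal rating sits solely on the less severe linked record. Chains of three or more records can instead be over-counted.

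The per-event effects are 8.3 points in one patient's LCRIS percentage (assuming all 12 doses) and 2 points in one discontinuation table (assuming 50 patients per group). The overall size is unknown, and a smaller apparent difference between doses should not be inferred. The conclusion assumes that sites open a new record at each change, as the SAP describes, and that programmers apply the definitions record by record. No primary or secondary efficacy result is affected. The SAP should be changed because the text as written can produce a wrong count and the repair is simple.

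**What to change.** Add a paragraph to SAP 3.7.2 that merges all Formlink-linked records into one episode, whatever the length of the chain, before any safety table is derived:

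- onset: first post-dose start, or the date of worsening in Case 1;
- end: last stop date, or ongoing;
- severity: highest on any record in the episode;
- serious: if any record is serious;
- related: if any record is rated related or possible, or has no rating;
- drug discontinued: if any record says so.

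Derive the TEAE, related, discontinuation, LCRIS and flu-like tables from the episode, and use episode onset for timing. State whether the two-day duration counts both end days. Retain the individual records in the listings.

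The cost is one SAP paragraph and one programming step, with no new data collection. It should be settled before treatment codes are opened for the primary analysis.

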9.4.2. Non-Serious Adverse Events

The recording of non-serious AEs will begin after the patient signs the informed consent form and will stop at the end of the patient's Follow-up Period, which is defined as Study Day 169. The Investigator will monitor each patient closely and record all observed or volunteered AEs on the Adverse Event Case Report Form.

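### The SAP's rules for treatment-emergent adverse events conflict with each other on missing end dates and on linked records, and can misclassify events that began before dosing

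*Combined protocol and SAP*

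**What the plan says.** Adverse events that precede treatment will be in the database. Protocol 9.4.2 states: "The recording of non-serious AEs will begin after the patient signs the informed consent form". Protocol 3.4.1 allows screening from Day -42 to Day -1.

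SAP 3.7.2 defines TEAEs as events that "either start or worsen in severity on or after the date/time of first dose of study treatment". Two sets of working rules follow.

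**Dates.** The complete-date rule applies "if the onset date or resolution date of an AE is prior to the first study treatment date"; such an event is classed as prior and so not treatment-emergent. The rule for incomplete dates opens "If the onset or resolution date of an AE is a partial date with only month or year available or complete missing, then the event". Its result is the reverse: the default is to place the event inside the study period, with an exception where the year precedes that of first dose or, in the same year, the month does. The sentence does not say which date supplies the year or month.

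**Linked records.** A change in severity opens a new record. Records are linked through the form-link "dataset and compared pairwise, and consider two cases, where the AE severity (mild/moderate/severe) are compared between the two records in the pair". In Case 1 (first record before dosing, second after), the second record is a TEAE if its severity or seriousness is worse. "Otherwise, neither record is considered as TEAE". In Case 2 (both records after dosing), the worse record is one TEAE. The resulting TEAEs feed an analysis of event numbers.

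**The concern.** The incomplete-date sentence is triggered by a missing resolution date alone, even when onset is fully known and precedes dosing. The sentence before it has already ruled on that event, the other way. The linked-record rules work on pairs, so in a chain of three or more records the middle one belongs to two pairs and can receive two verdicts. The SAP states no order of precedence in either place.

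TEAE incidence and severity is the first-named component of the safety endpoint (Protocol 1.2.3, SAP 1.3.3). If classification depends on how a programmer resolves contradictory sentences, the main safety tables are not fully prespecified, and events that began before treatment and never worsened have a route into them.

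**Working it through.** The plan gives no figure to reproduce, so the check applies the rules literally.

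**A. Dates.** Assume a first dose on 20 March 2022. The exception can be read on the incomplete date alone (reading 1) or on any available date (reading 2).

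| Onset | Resolution | Complete-date sentence | Incomplete-date sentence, reading 1 | Reading 2 |
|---|---|---|---|---|
| 5 Mar 2022 | missing | prior | within | within |
| 25 Feb 2022 | missing | prior | within | prior |
| 25 Feb 2022 | Apr 2022, no day | prior | within | prior |
| 30 Dec 2021 | missing | prior | within | prior |
| missing | 10 Mar 2022 | prior | within | within |
| 25 Feb 2022 | 2 Apr 2022 | prior | not triggered | not triggered |

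Rows 1 and 5 conflict on both readings, because the known date lies in the month of first dose. Rows 2 to 4 conflict only on reading 1. Row 6, with complete dates, has no conflict. For a first dose on day d of a month, d - 1 pre-dose days share that month. Here that is 20 - 1 = 19 of the 42 screening days.

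**B. Linked records.** Take severe (pre-dose), moderate (post-dose), mild (post-dose).
- Severe and moderate fall under Case 1. Moderate is not worse, so neither record is a TEAE.
- Moderate and mild fall under Case 2. Moderate is the worse, so it is a TEAE.

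The moderate record is both excluded and included, although the event only improved after dosing.

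Now list every chain over mild, moderate and severe in which consecutive records differ, comparing adjacent pairs on severity. There are 3 × 2 = 6 two-record and 3 × 2 × 2 = 12 three-record chains.
- One pre-dose, one post-dose: 3 of 6 do not worsen, and 0 of these 3 become TEAEs. Case 1 alone is correct on severity.
- Two pre-dose, one post-dose: 6 of 12 do not worsen, and 0 of these 6 become TEAEs.
- One pre-dose, two post-dose: 1 of 12 never worsens after dosing (the chain above), and it becomes a TEAE. Four more never exceed the pre-dose severity and become TEAEs, but each dips and then rises after dosing.
- All three post-dose: the 5 chains with the highest record in the middle give one TEAE. The other 12 - 5 = 7 give two.

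**C. Seriousness.** A pre-dose event that becomes serious at unchanged severity is a TEAE under Case 1. The definition, which mentions severity only, does not cover it.

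**The case against.** The strongest reply is that the SAP already contains the right exclusions: the complete-date sentence rules a pre-dose onset prior, and Case 1 excludes a record that did not worsen. The paragraph's appeal to conservatism is illustrated by that same complete-date rule, so using it to override the rule would turn the text against its own example. This stands. The text contradicts itself; it does not simply direct that such events be counted.

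Second, ongoing need not mean missing. Protocol 9.4.3.5 has an outcome for a persisting event, and SAP 3.7.2 treats ongoing as a status in its injection-site definition. This also stands: ongoing events are affected only if they are stored with no end date and that blank is treated as missing.

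Third, placing an event of unknown onset within the study period is an ordinary convention. Agreed. The trouble is confined to events for which a known date already settles the matter.

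Fourth, a programmer might treat exclusion in any pair as final. The severe, moderate, mild chain would then give no TEAE when it starts before dosing and one when it is wholly post-dose, as it should. But the SAP does not state that rule. On adjacent pairs it would also leave a double count wherever the middle record is lowest, because neither outer record is ever excluded: 4 chains with mild in the middle plus 1 with moderate, so 5 of the 7. The adjacent-pair reading is itself an inference, although the SAP's wording that the second record starts when the first stops favours it.

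Finally, the planned TEAE outputs are descriptive, and non-emergent events are noted in the listing. That limits the damage without removing the conflict.

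**Conclusion.** The concern holds as a conflict between stated rules that can misclassify events against the SAP's own definition. It is worth correcting, though its effect may be small.

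A reader might go further in three ways that the documents do not support.
- That the SAP counts unworsened pre-dose events as TEAEs outright. It also excludes them, so the outcome depends on which sentence is followed.
- That all 5 chains never exceeding the pre-dose severity are errors. Four of them worsen between post-dose records and fit the definition as written; only one is a contradiction.
- That the rules materially hide a drug effect. The documents give no adverse event counts, so any rate of affected events would be the reader's own assumption.

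For scale only: the design plans 150 × 1/2 × 2/3 = 50 patients per active dose and 2 × 150 × 1/2 × 1/3 = 50 on pooled placebo. One misclassified patient therefore moves a group's incidence by 1/50, or 2 percentage points. The rules apply equally to all arms, so the expected effect is slightly inflated TEAE counts and some dilution of differences, not a bias towards one arm. The double count affects event numbers only, because patients are tabulated once at their highest severity. It rests on comparing adjacent pairs.

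**What to change.** Amend SAP 3.7.2 before unblinding.

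1. **Dates.** Apply the incomplete-date assumption only when the onset date is partial or missing. Let a complete resolution date before first dose rule the event prior. State that an event with a known pre-dose onset is not a TEAE, whatever its end date, unless a linked post-dose record worsens. State which date supplies the year and month in the exception.
2. **Linked records.** Classify each chain once, with at most one TEAE. A chain that starts after dosing is one TEAE at its worst record. A chain that starts before dosing is one TEAE at its worst qualifying post-dose record, and none if no post-dose record worsens.
3. **Comparator.** State whether worsening is judged against the last pre-dose record or the preceding record. The current definition covers a post-dose dip and rise, so choosing the last pre-dose record would narrow it and should be a deliberate decision.
4. **Seriousness.** Bring the definition and Case 1 into line, either by adding seriousness to the former or by removing it from the latter.

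The cost is a few sentences and a small change to the TEAE derivation. No new data are needed. Reported TEAE counts may fall slightly.
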